- Complicated herpes zoster infection (with multi-dermatomal, disseminated, ophthalmic, or CNS involvement)
- Evidence of active HCV during the study, as evidenced by HCV RNA positivity
- Evidence of active HBV during the study, as evidenced by HBV DNA positivity
- Unacceptable toxicity, or toxicity that, in the judgment of the investigator, compromises the subject's ability to continue study-specific procedures or is considered to not be in the subject's best interest

- Treatment failure deemed by the investigator as lack of improvement or worsening of the disease symptoms or occurrence of intolerable AEs.
- Subject request to discontinue for any reason
- Subject noncompliance
- Pregnancy during the study (Section 8.8.1.2.1.5 and Appendix 13.8)
- Discontinuation of the study at the request of Galapagos, a regulatory agency or an institutional review board or independent ethics committee (IRB/IEC)
- Subject use of prohibited concurrent therapy *may* trigger study drug discontinuation; consultation should be made with the *medical monitor*.
- Laboratory criteria:

After becoming aware of any of the below described abnormal laboratory changes occurring at any one time, an unscheduled visit (ie sequential visit) should occur to retest within 3 to 5 days (except for creatinine, which should be retested 7-14 days later, unless medically indicated sooner).

- 2 sequential white cell counts <2000 cells/mm³ (SI: $<2.0 \times 10^9$ cells/L)
- 2 sequential neutrophil counts <1000 neutrophils/mm³ (SI: $<1.0 \times 10^9$ cells/L)
- 2 sequential lymphocyte counts <750 lymphocytes/mm³ (SI: $<0.75 \times 10^9$ cells/L)
- 2 sequential hemoglobin <8.0 g/dL (SI: <80 g/L)
- 2 sequential platelet counts $<75,000$ platelets/mm³ (SI: $<75.0 \times 10^9$ cells/L)
- 2 sequential aspartate aminotransferase (AST) or ALT elevations >3 times the upper limit of normal with at least one total Bilirubin value >2 times the upper limit of normal^a;
- 2 sequential AST or ALT elevations >3 times the upper limit of normal accompanied by symptoms consistent with hepatic injury^a;
- 2 sequential AST or ALT elevations >3 times the upper limit of normal accompanied by elevated INR;
- 2 sequential AST or ALT elevations >5 times the upper limit of normal, regardless of total Bilirubin or accompanying symptoms^a;
- 2 sequential values for estimate creatinine clearance <35 mL/min based on the Cockcroft Gault formula^b;

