- 2 sequential decreases from the baseline (of the core studies [GLPG0634-CL-203 or GLPG0634-CL-204]) of inhibin B by 50% with clinically relevant concurrent increase in FSH^c per investigator judgment. Note that this study drug discontinuation criterion applies only to subjects with baseline hormone levels within normal limits;
- 2 sequential decreases from the baseline (of the core studies [GLPG0634-CL-203 or GLPG0634-CL-204]) of testosterone by 50% with clinically relevant concurrent increase in LH, per investigator judgment^c. Note that this study drug discontinuation criterion applies only to subjects with baseline hormone levels within normal limits.

^a In each case, there is a need for additional investigations, such as review of ethanol, recreational drug and dietary supplement consumption; testing for acute hepatitis A, B or C infection and biliary tract imaging should be promptly discussed with the medical monitor.

^b If Creatinine Clearance has not been centrally reported, use the following: 2 sequential increases in serum creatinine >50% over the averaged of screening and baseline value (of the core studies [GLPG0634-CL-203 or GLPG0634-CL-204]).

^c In each case, hormones in male subjects should be monitored monthly and if no positive dynamics is seen after 3 months from stopping filgotinib, referral to an andrologist should be considered.

Subjects withdrawing from the study will be encouraged to complete the same final evaluations as subjects completing the study according to the protocol (please refer to Section 8.7.2.3 Final Visit or EDV), particularly safety evaluations in the subject's interest. The aim is to record data in the same way as for subjects who completed the study. Subjects are free to withdraw from the study at any time without providing reason(s) for withdrawal and without prejudice to further treatment. The reason(s) for withdrawal will be documented in the electronic case report form (eCRF).

Reasonable efforts will be made to contact subjects who are lost to follow-up. These must be documented in the subject's file.

The sponsor has the right to terminate the study at any time in case of safety concerns or if special circumstances concerning the study medication or the company itself occur, making further treatment of subjects impossible. In this event, the investigator(s) and relevant authorities will be informed of the reason for study termination.

The medical monitor should consult the medical leader as needed.

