8.9.1.3 Safety Variables

Clinical safety will be evaluated by assessing treatment-emergent AEs (TEAEs), physical examinations, laboratory assessments, ECG results, and vital signs results. The safety analysis may combine the data of all 3 studies (GLPG0634-CL-203, GLPG0634-CL-204, and GLPG0634-CL-205).

A treatment-emergent analysis of AEs will be done, based on the start date of the AE. TEAE (AE and SAE) preferred terms, intensity, frequency, relationship to study medication, dose reductions, and temporary/permanent treatment stops will all be tabulated. An additional analysis based on patient-years of exposure may be added when deemed useful.

Original results and changes from baseline will be summarized for all laboratory, vital signs, and ECG parameters, intended to detect any changes in safety parameters that could be attributed to GLPG0634 dosing. No imputations will be done for safety data in cases where subjects discontinued the study prematurely.

Further subgroup analyses (e.g., a selection of TEAEs with an onset date during the first weeks or months, or a division according to the mean actual dose) and exploratory analyses may be added when deemed appropriate.

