3.5.2. Analysis Visit Windows

Subject visits may not occur on protocol-specified days. Therefore, for the purpose of analysis, observations will be assigned to analysis windows for efficacy data in the core studies (Table 3-1 and Table 3-2) and GLPG0634-CL-205 (Table 3-3 and Table 3-4), and for non-efficacy data (Table 3-5). The analysis visit windows for non-efficacy data will be applied up to the last dose date of any study drug.

The baseline value is defined as follows:

Efficacy data:

- Core baseline: The last nonmissing value on or prior to the first dose date of study drug in the core studies
- Extension baseline: The last nonmissing value on or prior to the first dose date of study drug in GLPG0634-CL-205, and no earlier than the core study nominal Week 24 visit date

Safety data:

- Filgotinib baseline: The last nonmissing value on or prior to the first dose date of filgotinib in the core studies or GLPG0634-CL-205

Table 3-1. Analysis Visit Windows for Efficacy Data (SF-36 and FACIT-Fatigue Excluded) in the Core Studies

Analysis Visit	Nominal Study Day	Lower Limit	Upper Limit
Core Baseline	1	(none)	1
Core Week 1	8	2	11
Core Week 2	15	12	22
Core Week 4	29	23	43
Core Week 8	57	44	71
Core Week 12	85	72	99
Core Week 16	113	100	127
Core Week 20	141	128	155
Core Week 24	169	156	≥169

Table 3-2. Analysis Visit Windows for SF-36 and FACIT-Fatigue in the Core Studies

Analysis Visit	Nominal Study Day	Lower Limit	Upper Limit
Core Baseline	1	(none)	1
Core Week 4	29	2	57
Core Week 12	85	58	127
Core Week 24	169	128	≥169

Table 3-3. Analysis Visit Windows for Efficacy Data (SF-36 and FACIT-Fatigue Excluded) in GLPG0634-CL-205

Analysis Visit	Nominal Study Day	Lower Limit	Upper Limit
Extension Baseline	1	(none)	1
Extension Week 12	85	2	127
Extension Week 24	169	128	211
Extension Week 36	253	212	295
Extension Week 48	337	296	379
Extension Week 60	421	380	463
Extension Week 72	505	464	547
Extension Week 84	589	548	631
Extension Week W	7xW+1	7xW-40	7xW+43

Table 3-4. Analysis Visit Windows for SF-36 and FACIT-Fatigue in GLPG0634-CL-205

Analysis Visit	Nominal Study Day	Lower Limit	Upper Limit
Extension Baseline	1	(none)	1
Extension Week 48	337	2	505
Extension Week 96	673	506	841
Extension Week W	7xW+1	7xW-166	7xW+169

Table 3-5. Analysis Visit Windows for Non-Efficacy Data

Analysis Visit	Nominal Study Day	Lower Limit	Upper Limit
Filgotinib Baseline	1	(none)	1
Week 12	85	2	127
Week 24	169	128	211
Week 36	253	212	295
Week 48	337	296	379
Week 60	421	380	463

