Week 72	505	464	547
Week 84	589	548	631
Week W	7xW+1	7xW-40	7xW+43

CRP measured on or after nominal follow up visit will not be assigned analysis window and summarized, but will be included in the listing.

Vital signs, ECG, and safety laboratory data collected in the follow up period will also be summarized. The analysis window for the post-treatment follow-up period is defined as from (last dose date of filgotinib + 1 day) to (last dose date of filgotinib + 30 days). If multiple valid, nonmissing measurements exist in the post treatment follow-up visit window, the latest record will be selected for analysis. If the chronological order cannot be determined, for any given subject, the value with the worst severity will be selected for categorical variable, and the average will be taken for continuous variable. Data obtained after last dose date plus 30 days will be excluded from the summaries, but will be included in the listings.

3.5.3. Selection of Non-Efficacy Data in the Event of Multiple Records in an Analysis Visit Window

Depending on the statistical analysis method, single values may be required for each analysis window. For example, change from baseline by visit usually requires a single value, whereas a time-to-event analysis would not require 1 value per analysis window.

If multiple valid, nonmissing, continuous measurements exist in an analysis window, records will be chosen based on the following rules if a single value is needed:

- In general, the filgotinib baseline value will be the last nonmissing value on or prior to the first dose date of filgotinib in the core studies or GLPG0634-CL-205, unless otherwise specified. If multiple measurements occur on the same day, the last nonmissing value prior to the time of first dose of filgotinib in the core studies or GLPG0634-CL-205 will be considered as the filgotinib baseline value. If these multiple measurements occur at the same time or the time is not available, the average of these measurements (for continuous data) will be considered the filgotinib baseline value.
- For postbaseline visits:
 - The record closest to the nominal day for that visit will be selected.
 - If there are 2 records that are equidistant from the nominal day, the later record will be selected.
 - If there is more than 1 record on the selected day, the average will be taken, unless otherwise specified.

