7.2.1. Summaries of Numeric Laboratory Results

Descriptive statistics of filgotinib baseline values, values at each postbaseline visit and change from filgotinib baseline at each post baseline visit will be provided by treatment group for the following laboratory tests:

- Hematology
 - Hematocrit
 - Hemoglobin
 - Platelet count
 - Red blood cell count
 - White blood cell (WBC) count

- Lymphocytes
- Monocytes
- Neutrophils
- Eosinophils
- Basophils
- Chemistry
 - Alanine aminotransferase (ALT)
 - Aspartate aminotransferase (AST)
 - Alkaline phosphatase (ALP)
 - Total bilirubin
 - Serum creatinine
 - Creatinine clearance by Cockcroft-Gault formula
 - Glucose
- Lipid
 - Triglycerides
 - Total cholesterol
 - HDL
 - LDL
 - LDL/HDL ratio
- Hormone in male subjects
 - Follicle stimulating hormone
 - Inhibin B
 - Luteinizing hormone
 - Testosterone

A filgotinib baseline laboratory value will be defined as the last measurement obtained on or prior to the date/time of first dose of filgotinib in the core studies or GLPG0634-CL-205. Change from filgotinib baseline to a postbaseline visit will be defined as the visit value minus the filgotinib baseline value. The mean, median, Q1, Q3, minimum, and maximum values will be displayed to the reported number of digits; SD values will be displayed to the reported number of digits plus 1.

Median (Q1, Q3) of the observed values for the laboratory tests specified above will be plotted using a line plot by treatment group and visit.

In the case of multiple values in an analysis window, data will be selected for analysis as described in Section 3.5.3.

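### The SAP summarises male hormones only by visit, so no planned output shows how many men had a 50% fall in inhibin B or testosterone, the size of fall on which the protocol's stopping rule turns

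*Protocol*

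**What the plan says.** **Stopping rule (Protocol 8.4.2).** Two of the laboratory criteria apply to men. One is two sequential decreases from the core-study baseline "of inhibin B by 50% with clinically relevant concurrent increase in FSH". The other is the same rule for testosterone with LH. Both leave the clinical relevance of the FSH or LH rise to the investigator, and both apply only if baseline hormones were normal. After an abnormal laboratory change, "an unscheduled visit (ie sequential visit) should occur to retest within 3 to 5 days". Footnote c adds: "In each case, hormones in male subjects should be monitored monthly", with andrology referral to be considered if there is no improvement three months after stopping.

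**Purpose of the laboratory summaries (Protocol 8.9.1.3).** They are "intended to detect any changes in safety parameters that could be attributed to GLPG0634 dosing". Also, "No imputations will be done for safety data in cases where subjects discontinued the study prematurely".

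**Planned hormone analysis (SAP 7.2.1).** FSH, inhibin B, LH and testosterone get by-visit mean, SD, median, quartiles, minimum and maximum, for values and for change. Change is the visit value minus the filgotinib baseline. In addition, "Median (Q1, Q3) of the observed values for the laboratory tests specified above will be plotted".

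**Records used (SAP 3.5.2 and 3.5.3).** "The analysis visit windows for non-efficacy data will be applied up to the last dose date of any study drug". Where a window holds several values, "The record closest to the nominal day for that visit will be selected". A separate post-treatment window runs from day 1 to day 30 after last dose. Later data are listed but not summarised.

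**Subject-level counts (SAP 7.2.2 and 7.2.3).** Section 7.2.3 covers AST, ALT and bilirubin multiples and CTCAE shifts in five blood counts. Section 7.2.2 grades laboratory results by CTCAE without saying which tests are graded. The SAP 7.2 listing names hematology, serum chemistry and urinalysis.

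**The concern.** The stopping rule concerns each man's proportional fall from his own baseline. The planned summary describes the distribution of absolute values and absolute changes across men at each visit. The second does not yield the first.

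The question matters in this trial. Long-term safety is the primary objective. Protocol 6.3.4 reports animal testicular toxicity that was only partly reversible, and Protocol 6.5 names the testes as a target organ. SAP 1.2 says that US men were limited to 100 mg once daily because of this signal, and Protocol 10.4 requires that infertility risk be discussed with every man. The human hormone data cited in Protocol 6.4 are group-level changes over 24 weeks in CL-203, whereas this study samples male hormones every 12 weeks for about 96 months. It is well placed to say how often an individual man's hormones halve, yet no planned table or listing would say so.

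**Working it through.** **1. Can any planned output give the count?**

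| Output | Why it does not give the number of men with a 50% fall |
|---|---|
| SAP 7.2.1 by-visit statistics | Change is absolute, so even the minimum change does not identify a 50% fall. Men are not accumulated across visits. |
| SAP 7.2.1 plot | Shows median and quartiles only. |
| SAP 7.2.2 graded abnormalities | Tests graded are not named; a grade shift is not a 50% fall. |
| SAP 7.2.3 | Liver tests and blood counts only. |
| SAP 7.2 listing | Hormones not named. Protocol 8.8.1.2.2 and SAP 7.2.1 both place them outside chemistry. |
| SAP 4.1 disposition; SAP 7.1.6.1 adverse events leading to discontinuation | Reach some stopped men, but not as hormone falls, and miss men who fell 50% without stopping. |

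**2. Is the confirmation visible?** The general window in SAP Table 3-5 runs from day 7W−40 to 7W+43, which is 43 + 40 + 1 = 84 days. A retest 3 to 5 days after the site learns of the result normally falls in the same window as the first sample, where one record is kept. The pair is then not seen.

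**3. Is recovery visible?** Monthly samples at about days 30, 60 and 90 after stopping put at most one of three inside the 30-day window.

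**4. Is the baseline the same?** The stopping rule uses core-study baseline; SAP 7.2.1 uses filgotinib baseline. These can differ for men who began a core study on placebo.

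**5. Illustrative size.** The only stated design figure reproduces: 0.7 × (595 + 280) = 612.5, given as 612. It does not bear on this point. 739 were enrolled and the number of men is not given. Assume 10%, 20% or 30%: 74, 148 or 222 men.

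- Shift in the visit mean from one man of average level with a 60% fall: 60/N = 0.81%, 0.41%, 0.27%.
- SE of the mean change, as a percentage of the mean, with within-man noise on both samples: 100 × √[2·w²·(1 + b²)/N], where b is the between-man CV (assumed 30% to 50%) and w the within-man CV (assumed 15% to 25%). At N = 148, the low end is 100 × √(2 × 0.0225 × 1.09/148) = 1.8% and the high end is 100 × √(2 × 0.0625 × 1.25/148) = 3.2%. For N = 74 the range is 2.6% to 4.6%; for N = 222, 1.5% to 2.7%.
- In a lognormal simulation under these assumptions, that man supplies the visit's minimum change in about 5% to 47% of runs across the three sizes. The displayed minimum is therefore not a dependable marker.
- If 4 of 148 men had a 50% fall at the same visit, the mean would move by 50 × 4/148 = 1.4%, still below one SE. A count would report 2.7% (exact 95% CI 0.7% to 6.8%).
- If no man had such a fall, the two-sided 95% upper limit is 1 − 0.025^(1/N) = 4.86%, 2.46% or 1.65%.

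**The case against.** The strongest reply is that no commitment is broken. Protocol 8.9.1.3 promises results and changes from baseline for laboratory parameters, and the SAP delivers these for four hormones. The study is descriptive and uncontrolled, and the protocol allows exploratory analyses to be added. That stands. It makes this an improvement to the plan rather than a departure from the protocol, but an optional analysis is not a planned one.

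Several stronger readings are tempting and are not supported:

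- *Stopped men disappear from the tables.* SAP 3.5.1 takes the Final Visit or Early Discontinuation Visit date as the last dose date, so hormones drawn at that visit are inside the treatment windows. The 30-day post-treatment window can also take the Follow-up Visit sample. These men are missing only from later visits, as is any subject who stops.
- *Later visits contain only men without a confirmed fall.* A man with a confirmed fall but no relevant FSH or LH rise, or with abnormal baseline hormones, does not meet the rule and can stay on drug and in every table.
- *The SAP counts stopping events for other analytes and omits hormones.* Section 7.2.3 reproduces no complete stopping criterion. Its blood counts use CTCAE grades rather than the protocol's cell limits, and nothing there requires two sequential values. The contrast is only that those analytes get some subject-level abnormality count and hormones get none.
- *Hormones get means and medians only.* SD, quartiles, minimum and maximum are planned too.
- *Stopped men are invisible.* Discontinuation reasons are tabulated and listed, and a hormone fall recorded as an adverse event leading to discontinuation would appear there.

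**Conclusion.** The point holds. The planned outputs cannot say how many men had a 50% fall in inhibin B or testosterone, how many had it confirmed, or how many met the stopping rule. This follows from the documents and needs no assumption.

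The size is illustrative only. At an assumed 148 men, a single 60% fall moves a visit mean by about 0.4% against an SE of about 1.8% to 3.2%, and 0/148 would cap the proportion at about 2.5%. The number of men, both CVs and the depth of the fall are assumed. The limit is on a crude proportion over unequal follow-up, not on a rate, and it widens if fewer men have normal baseline hormones: if only 74 of the 148 qualified, it would be 4.86%.

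A reader might infer that hormone falls are occurring and being missed. Nothing in the documents shows that; Protocol 6.4 reports small testosterone increases and small mixed changes in the other hormones in CL-203. The finding is that this study, as planned, would not report such falls if they occurred, nor put a limit on them if they did not. The change should be made.

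**What to change.** Add a male-hormone subsection to SAP 7.2.3. Among men with normal core-baseline hormones and at least one postbaseline value, give n (%) with exact 95% CI, by group and overall, for:

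- (a) any fall of 50% or more from core baseline in inhibin B, and separately in total testosterone;
- (b) such a fall confirmed on two sequential samples, using all records, including unscheduled ones, up to last dose + 30 days;
- (c) a confirmed fall with a concurrent rise from core baseline in FSH (for inhibin B) or LH (for testosterone), flagging values above the reference range. This is descriptive, because the protocol leaves clinical relevance to the investigator and a relevant rise may stay within range.

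Report also the number of men stopped under either criterion. In SAP 7.2, add male hormones to the by-subject listing, including values after day 30, so that any recorded footnote c monitoring can be seen.

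**Cost.** One table and one listing panel from hormones already sampled every 12 weeks; no new visit, blood draw or protocol amendment. The drawbacks are that the table is uncontrolled and descriptive, and that (a) will include transient falls, which is why (b) and (c) are shown separately.

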MTX	=	methotrexate
NOAEL	=	no-observed-adverse-effect-level
NOEL	=	no-observed-effect-level
NSAID	=	non-steroidal anti-inflammatory drug
PD	=	pharmacodynamic
PK	=	pharmacokinetic
PRL	=	prolactin
q.d.	=	quaque die (once daily)
RA	=	rheumatoid arthritis
RBC	=	red blood cell
SAE	=	serious adverse event
SDAI	=	simplified disease activity index
SF-36	=	36-item short-form health survey
SJC	=	swollen joint count
SMPC	=	Summary of Product Characteristics
SQRT	=	square root
STAT	=	signal transducer and activator of transcription
t _{1/2}	=	terminal half-life
TB	=	tuberculosis
TEAE	=	treatment-emergent adverse event
TJC	=	tender joint count
t _{max}	=	time to maximum plasma concentration
TNF	=	tumor necrosis factor
TYK	=	tyrosine kinase
UGT	=	uridine 5'-diphosphate glucuronosyltransferase
VAS	=	visual analog scale
WBC	=	white blood cell

Cockcroft-Gault CrCl Formula = $[(140 - \text{age}) \times (\text{Wt in kg}) \times (0.85 \text{ if female})] / (72 \times \text{Cr})$
Wt = Weight in Kilograms
Cr = Creatinine in mg/dL

6 Introduction

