8.3.3 Exclusion Criteria

Subjects will be excluded from the study if one or more of the following statements are applicable:

1. Subjects who had been prematurely withdrawn from one of the 2 core studies (GLPG0634-CL-203 or GLPG0634-CL-204), for any reason, including fulfilling the individual stopping criteria.
2. Subjects who are deemed not to be benefiting from the study medication based upon lack of improvement or worsening of their symptoms. Local guidelines for subject treatment need to be followed.
3. Subjects with persistent abnormal laboratory values, associated with the use of the study medication (including but not limited to hematology, liver and renal function values) during one of the 2 core studies (GLPG0634-CL-203 and GLPG0634-CL-204), according to the investigator's clinical judgment.
4. Subjects who require immunization with live/live attenuated vaccine.

5. Subjects with diagnosis since the inclusion to GLPG0634-CL-203 or GLPG0634-CL-204 core studies of rheumatic autoimmune disease or inflammatory joint disease other than RA, except for secondary Sjögren's syndrome.
6. Subjects with symptoms suggestive of moderate to severe congestive heart failure or major cerebrovascular event since the inclusion to GLPG0634-CL-203 and GLPG0634-CL-204 core studies.
7. Subjects with symptoms suggestive of GI tract ulceration and/or active diverticulitis since the inclusion to GLPG0634-CL-203 and GLPG0634-CL-204 core studies.
8. Subjects with symptoms suggestive of possible lymphoproliferative disease including lymphadenopathy or splenomegaly since the inclusion to GLPG0634-CL-203 and GLPG0634-CL-204 core studies.
9. Subjects with symptoms suggestive of malignancy since the inclusion to GLPG0634-CL-203 and GLPG0634-CL-204 core studies.
10. If applicable to national or local legislation: history of being admitted to an institution under administrative or court order since the inclusion to GLPG0634-CL-203 and GLPG0634-CL-204 core studies.
11. History of drug and alcohol abuse since the inclusion to GLPG0634-CL-203 and GLPG0634-CL-204 core studies.
12. Any condition or circumstances which, in the opinion of the investigator, may make a subject unlikely or unable to complete the study or comply with study procedures and requirements.

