8.7.1.1 Entry Visit (Extension Visit 1, Day -1)

The Entry Visit (Visit 1) will take place on Day -1 relative to the start of the study medication intake. There will be no gap between the core studies and the open-label extension study.

- Subjects will be assessed for eligibility against the inclusion and exclusion criteria.
- Entry Visit data will be those collected at the Week 24 visit from the previous core study in which the subject has participated (GLPG0634-CL-203 or GLPG0634-CL-204) for physical examination, 12-lead ECG, vital signs, clinical laboratory tests (including serum pregnancy test), SJC66, TJC68, Physician's Global Assessment, Patient's Global Assessment, health assessment questionnaire – disability index (HAQ-DI), FACIT fatigue scale, and SF-36 questionnaire. Data on demographics, baseline characteristics, and medical history will be retrieved from the

Screening visit of the previous core studies. Data will not be re-entered in the GLPG0634-CL-205 eCRF but will be retrieved from the preceding core study database during statistical programming.

- Urine (dipstick) pregnancy test for females of childbearing potential.
- Tuberculosis (TB) blood test (QuantiFERON-TB gold test^a) will be performed.
- Any new AEs that have occurred since signing the informed consent form (ICF) will be documented.
- Any ongoing or unresolved AEs and concomitant medications from the preceding core study will be documented on the GLPG0634-CL-205 AE and concomitant medication pages of the eCRF, respectively.
- IXRS call.

^a In case of a positive or confirmed indeterminate result for QuantiFERON-TB gold test: 1.) Permanent withdrawal of the subject from the study; 2.) Consultation with the local infectious disease specialist is highly recommended to investigate if the patient has active or latent TB or no TB

When all the Entry Visit procedures have been performed and the investigator has confirmed the subject's eligibility for the study, the study medication will be dispensed to the subject. The subject will start taking the study medication on Day 1 and subsequent visits will be scheduled.

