8.7.2.1 Quarterly Evaluation Visit (QEV)

A QEV visit will take place every 12 weeks \pm 1 week relative to the start of the study medication intake.

- Subjects will be assessed for eligibility against the withdrawal criteria.
- Any remaining study medication as well as empty study medication containers will be returned to the investigator and an accountability check performed.
- A physical examination will be performed.
- Weight is measured at all visits.

- A 12-lead ECG will be performed.
- Any AEs that have occurred since signing the ICF will be documented and any changes in concomitant medication reported.
- Vital signs will be measured.
- Hematology, clinical chemistry, hormones (for male subjects only), and urinalysis (dipstick and, in case of abnormal dipstick result, microscopy) tests will be performed on samples collected at this visit. A urine pregnancy test will be performed on females of childbearing potential.
- Serum CRP will be measured.
- SJC66 and TJC68 evaluations will be performed.
- Physician's and Patient's Global Assessments of Disease Activity will be completed.
- The subject will complete the HAQ-DI.
- IXRS call.

When all of these procedures have been performed, the study medication will be dispensed, and the date of the next visit confirmed.

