8.8.1.2.2 Clinical Laboratory Evaluation

The hematology and clinical chemistry laboratory analyses will be performed at a central laboratory ██████████. Reference ranges will be supplied by the central laboratory and used by the investigator to assess the laboratory data for clinical significance and pathological changes.

The total amount of blood to be taken at the AV will not exceed 43 mL.

The total amount of blood to be taken at Entry Visit, QEV, Final Visit/EDV and Follow-up Visit will not exceed 39 mL.

The following laboratory safety tests will be performed at every visit:

Hematology

Hemoglobin, hematocrit, WBC count (total and differential), RBC count, differential lymphocyte count (by flow cytometry: CD3, CD19, CD4, CD8, CD3-/CD16+, and CD56+), platelet count, activated partial thromboplastin time, and prothrombin time.

Clinical Chemistry

Creatinine, blood urea nitrogen, aspartate aminotransferase, ALT, gamma-glutamyltransferase, alkaline phosphatase, total bilirubin, amylase, lipase, albumin, total protein, sodium, potassium, chloride, glucose, uric acid, total cholesterol, HDL- and LDL-cholesterol, triglycerides, calcium, and phosphorus.

Serum CRP will be measured at every visit except the Follow-up Visit.

Serum pregnancy test for females of childbearing potential is performed at the AV, Final Visit/EDV and the Follow-up Visit.

Hormone tests (for male subjects only)

Testosterone (total and free), LH, FSH, PRL, and inhibin B.

Urinalysis

pH, glucose, ketone bodies, indicators of blood and WBC, and protein (quantitative).

Urine pregnancy test for females of childbearing potential is performed at Entry Visit and QEV, and also performed every 4 weeks during the dosing period through 35 days after their last dose of study drug using home pregnancy tests that will be provided to them. Refer to Appendix 13.8 for details.

Other

TB blood (QuantiFERON-TB Gold) test at Entry Visit and AV.

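### When creatinine clearance is not centrally reported, the fallback stopping rule can leave a subject below the protocol's own 35 mL/min limit with no numeric trigger

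*Protocol*

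**What the plan says.** Among the laboratory criteria for permanent discontinuation, Protocol section 8.4.2 lists "2 sequential values for estimate creatinine clearance <35 mL/min based on the Cockcroft Gault formula". Footnote b to that line reads "If Creatinine Clearance has not been centrally reported, use the following: 2 sequential increases in serum creatinine >50"% over the average of the screening and baseline values from the core study (GLPG0634-CL-203 or GLPG0634-CL-204).

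The early retest depends on one of the listed abnormalities being seen first. The general window is 3 to 5 days, "except for creatinine, which should be retested 7-14 days later, unless medically indicated sooner".

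The inputs for a clearance calculation are already available:

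- Section 5 prints the "Cockcroft-Gault CrCl Formula".
- Section 8.8.1.2.2 states "The hematology and clinical chemistry laboratory analyses will be performed at a central laboratory". Its every-visit chemistry panel names creatinine but not clearance.
- Section 8.7.2.1 states "Weight is measured at all visits".
- Section 8.7.1.1 takes demographics from the core-study screening visit.

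SAP section 7.2.1 plans to summarise Cockcroft-Gault clearance by visit, so the quantity will be derived for analysis in any case.

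**The concern.** The main criterion is an absolute floor on renal function. The fallback is a relative rise in creatinine from a fixed early value. The footnote's wording makes it a substitute for the floor, not an addition to it, and no text tells a site to compute a clearance that the laboratory did not supply. The two rules protect different people. A relative rule acts early in subjects with good renal function and late in those who start close to the limit.

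Where the fallback applies, a subject with low baseline clearance can therefore be under 35 mL/min without meeting the stated condition for a retest or a stop. The fallback also cannot register the fall in calculated clearance that comes with age, and the open-label period is about 96 months (section 8.1). What is at stake is a patient-safety rule. No endpoint or planned analysis depends on it.

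**Working it through.** The documents give no figure to reproduce here: 35 mL/min and 50% are chosen thresholds. All baseline clearances, ages and weights below are assumptions.

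**Formula (Protocol section 5).** Clearance = (140 − age) × weight × (0.85 if female) / (72 × creatinine in mg/dL). At fixed age, sex and weight, current clearance = baseline clearance × (baseline creatinine / current creatinine).

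**Crossover.** The fallback acts when creatinine exceeds 1.5 times its reference, that is, when clearance falls below baseline / 1.5. This equals 35 when baseline = 35 × 1.5 = 52.5 mL/min. The rise at which the main rule acts is baseline / 35 − 1. With both rules in force, clearance at the first trigger is max(35, baseline / 1.5).

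| Baseline clearance (mL/min) | Clearance when fallback acts | Creatinine rise that reaches 35 | First trigger with both rules |
|---|---|---|---|
| 40 | 26.7 | 14% | 35 |
| 45 | 30.0 | 29% | 35 |
| 50 | 33.3 | 43% | 35 |
| 52.5 | 35.0 | 50% | 35 |
| 60 | 40.0 | 71% | 40.0 |
| 80 | 53.3 | 129% | 53.3 |
| 100 | 66.7 | 186% | 66.7 |

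Below 52.5 the fallback is the later rule; above it, the stricter one.

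**Worked example.** Take a woman of 65 years, 60 kg, creatinine 1.2 mg/dL. Clearance = 75 × 60 × 0.85 / (72 × 1.2) = 3825 / 86.4 = 44.3 mL/min. A sustained 40% rise to 1.68 mg/dL gives 3825 / 120.96 = 31.6 mL/min. The main rule stops her; the fallback does not.

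**Ageing over 8 years, constant weight.** Clearance at unchanged creatinine is multiplied by r = (132 − age) / (140 − age), with age taken at core baseline. The crossover becomes 52.5 / r, and a baseline of 35 / r reaches 35 with no creatinine change.

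| Age at core baseline | r | Crossover 52.5 / r | Baseline reaching 35 with unchanged creatinine |
|---|---|---|---|
| 45 | 0.916 | 57.3 | 38.2 |
| 55 | 0.906 | 58.0 | 38.6 |
| 65 | 0.893 | 58.8 | 39.2 |
| 75 | 0.877 | 59.9 | 39.9 |

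**Other sensitivities, no ageing.** A 10% weight loss moves the crossover to 52.5 / 0.9 = 58.3, and a 10% gain to 52.5 / 1.1 = 47.7. The fallback reference averages two creatinine values. If the screening value is 10% below or above the baseline-visit value, the crossover expressed as baseline-visit clearance is 52.5 × 0.95 = 49.9 or 52.5 × 1.05 = 55.1.

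**Check of the remedy.** On a grid of baseline clearances 36–120 and creatinine ratios 1.00–4.00, 15,094 combinations fall below 35. The fallback alone leaves 421 without a trigger, all at baselines below 52.5. With both rules none is left. These are grid points, not patient frequencies.

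**The case against.** The strongest objection is that the exposed group may be empty. Harm needs three things together: a low baseline clearance, a clearance that was not reported, and a creatinine rise that crosses 35 without exceeding 50%. The documents give neither the core studies' renal entry limits, nor the baseline distribution, nor the non-reporting rate. If the core studies excluded clearances below about 53, the fixed-age gap disappears; below about 60, so does the ageing version at constant weight. Section 6.5 describes the phase 2b creatinine rises as mild and stable by Week 24. All of this stands, and it limits the weight of the point.

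Other safeguards also remain:

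- Entry exclusion of persistent drug-associated laboratory abnormalities, "including but not limited to hematology, liver and renal function values" (section 8.3.3).
- Investigator judgment of toxicity (section 8.4.2).
- Local methotrexate monitoring (section 8.6.8).
- Investigator review of central results (section 8.8.1.2.2).
- Ongoing sponsor safety review (section 8.9.1.5).

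Creatinine is measured again at the next 12-weekly visit, so what is lost is the early 7–14 day retest, and the main rule returns if clearance is reported then. None of these safeguards, however, sets a clearance floor for filgotinib, and a repeat creatinine judged by the same fallback adds no new trigger.

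It can also be said that calculating clearance closes the gap alone, so keeping the 50% rise is unnecessary and leaves two standards. A baseline of 80 would stop at 53.3 if the site calculated clearance, but only below 35 if the laboratory reported it. That difference already exists under footnote b. Keeping the 50% rise avoids loosening the present rule for subjects above the crossover.

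**Conclusion.** The point holds. Followed exactly, footnote b can keep a subject on filgotinib below the protocol's own 35 mL/min limit with no numeric trigger for an early retest or stop. The affected baselines are below 52.5 mL/min at fixed age and weight, with baseline clearance taken from the averaged core-study creatinine. After eight years at constant weight the limit is about 57–60 mL/min for core-baseline ages 45–75. From an assumed baseline of 40 the delay at fixed age is from 35 down to 26.7 mL/min.

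The number of subjects exposed cannot be estimated from the documents and may be zero. No harm is demonstrated. This is a worthwhile, cheap improvement to a stated safety rule, held with medium confidence because the exposure is unknown.

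**What to change.** Amend footnote b in section 8.4.2. If clearance is not centrally reported, calculate it with the section 5 formula from the creatinine result (in mg/dL), current age, sex and latest measured weight, and apply the rule of two sequential values below 35 mL/min. In these cases keep the creatinine rise above 50% as an additional trigger, not a replacement. The 35 mL/min rule alone would miss, for example, a baseline of 100 with doubled creatinine (clearance 50). Whether the 50% rise leads to discontinuation, as now, or to medical-monitor review is for the sponsor's clinicians, but it should not be dropped.

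The cost is one footnote and one calculated field, with the ethics approval that any protocol change needs (section 10.1) and some care over units and weight entry. There may be a few more retests, reviews or discontinuations in subjects with low clearance. If the 50% rise remains a stop, nobody has a looser rule than today. If it becomes a review, subjects above the crossover would be reviewed at that point instead of stopped.
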